Analysis Issues: *SPSS Data Entry*⁽¹⁴⁸⁾ will be used as the data management system for the project's telephone interviews. A computer-assisted telephone interview (CATI) program will be developed by an experienced programmer from the Indiana University School of Medicine Division of Biostatistics. For each field of entry, ranges will be set to accept only legitimate responses, and skip patterns will be programmed to make the interviews more accurate.

Limitations of This Study and Analyses to Address Limitations: The proposed study is designed to achieve the specific aims and test the hypotheses. However, several limitations are listed below along with explanations of our efforts to minimize the limitations.

- **Loss to follow-up:** Although we will attempt to retain subjects who complete the baseline telephone interview through the 6-month follow-up interview, there will be attrition because of participant dropout, death, and moving. We are conservatively estimating a 10% loss to follow-up although we expect it to be closer to our previous studies of 5% over a 6-month period. When analyses are performed to examine criterion variables at any given time point, all subjects who have data at that point will be included, minimizing the effects of loss of subjects because of later drop-out. In addition, the primary outcome variables, mammography and CRC cancer screening adherence, will be available through electronic records audit. As long as women drop out at a similar rate in both intervention groups, the threat to internal validity of dropout bias will be minimal (in addition, see Missing Data below). Additionally, we expect a low drop-out rate. It should be noted that attrition was accounted for in the sample size determination and power analysis.

- **Missing data and methods for handling in analyses:** Missing data should be minimized by the use of telephone data collection and through interviewer training. Based on our previous work, we expect no more than 1-2% missing data for any single variable. Missing data for the major variables of CRC and breast cancer screening adherence (claims data) will be of concern if a woman changes health insurance plans. If a woman changes plans, we will still collect 6-month self-report data and inquire as to whether she has received either CRC or BC screening at another location. Because enrolled women will have signed informed consent to access claims data, we will be able to obtain CRC screening mammography records even in the event that health care plans have changed. We will examine reasons for drop-out and compare baseline characteristics of those with complete data versus those with missing data. If data are 'missing at random' (MAR) estimates will be biased and if 'missing completely at random' (MCAR) estimates will be inefficient if models are not adjusted for missingness. Therefore, we will use multiple imputation to perform adjustment for missingness. We will also perform sensitivity analyses to see how the results might have been affected under various assumptions had the data been available. The sensitivity analysis will also include estimating models while stratifying on the categories of missing data patterns,⁽¹⁴⁹⁾ although the multiple imputation method will be considered the more authoritative adjustment. Because patients will be randomized after they receive their baseline assessment, there are three possible missing data patterns (i.e., missing 2-week assessment, missing 6-month assessment, or missing both 2-week and 6-month). Furthermore, claims data will make it

possible to analyze adherence at 6 months even for women who dropped out, as long as claims data for those women can be obtained.

- **Sample bias:** We conservatively estimate that about 50% of contacted women will consent to participate, and women who are interested in CRC or BC screening may self-select into the study. Contacting only nonadherent women will minimize this bias.
- **Feasibility/Clinical Relevance:** Either of the intervention strategies tested in the proposed project could easily be adapted into routine practice, if found effective. Previous studies have tailored interventions on a large number of variables necessitating lengthy interviews (Preliminary Studies). In contrast, the proposed interventions will be tailored on fewer variables and in an interactive format, thus facilitating data collection at baseline and “batch processing” the intervention. The TIWeb could even be distributed during routine care visits if a recent mammogram or CRC screening is not recorded on the chart. The addition of a CSC call from the provider’s office could also be incorporated into practice if found to have an additive value to the TIWeb.

E. Human Subjects

1. Risks to Subjects

Human Subjects Involvement and Characteristics. Participants in this study will be eligible if they have ever been a patient of any of the participating physicians; are age 50 to 75; are nonadherent to CRC or CRC and BC screening; and are able to complete telephone surveys and, depending on intervention, view a TIWeb, view a TIWeb and receive a counseling call, or receive usual care. Women will not be eligible if they have a history of adenomatous polyps, a personal history of CRC, inflammatory bowel disease or an hereditary syndrome (HNPCC\FAP). Eligibility criteria will be determined from both database records and self-report. Because this project involves mammography utilization, only women will be included.

Source of Materials: Data will be obtained from self-report at baseline and at 4-week and 6-month follow-up. Mammography status and CRC screening will be obtained from medical record data as well as self-report. Cost data will be obtained from the study administrative records.

Potential Risks: The proposed investigation does not present physical risk. Emotional or psychological risks, if they occur, would be slight. Possible fear or anxiety may be elicited when asking questions about BC,mammography, and/or colon cancer screening.

2. Adequacy of Protection against Risks

Recruitment and Informed Consent: Recruitment of subjects follows a plan that complies with the HIPAA requirements. Eligible women will be identified by the INPC, Community Health Network, any of the participating physicians, or their designee. The research office will send each potentially eligible woman a letter explaining the study and including a brochure and refusal postcard. Women will also receive a refusal postcard to send back if they choose not to be contacted. They can also refuse by calling a toll free number or emailing the project manager (this information found on the brochure). They can also call the toll-free telephone number provided on the brochure to call should they have questions. If women have not returned the refusal postcard, called, or emailed to decline within two weeks, they will be put on the schedule for a recruitment call. In order to tell whether or not the two week opt out period is sufficient time for women to opt out, the PI and project manager will monitor a spreadsheet that will be developed for tracking calls made by study staff to women who indicate that they did opt out of the study by returning the refusal postcard, calling the toll free number, or emailing the project manager. If a woman indicates that she did opt out the study staff will apologize and indicate to the project manager or PI that this has happened. The project manager will then make sure her documentation is destroyed. Once this occurrence has happened a total of ten times, the PI will reevaluate the opt out time period and consider revising. Any occurrences will be reported to the IRB at continuing review. Research assistants will attempt to contact each woman by phone to further explain the study. If a woman indicates that she does not want to participate, she will be thanked for her time and no further contact will be made. If a woman agrees to participate, we will obtain verbal consent for a baseline telephone or electronic interview that will be conducted at the time of contact if convenient or within one week. The components of consent are listed on the brochure and include the right to terminate the study at any time without changes in health care. An authorization form to access medical records will be available for the

participant to sign electronically. The entire process of the study will be explained including the possibility of being assigned to one of two groups, the 4-week and 6-month telephone interviews, and the need to obtain mammography records.

Protection against Risk: Interviewers and research assistants delivering the CSD will be graduate research assistants in a health-related field who will be trained to detect unwarranted anxiety or fear. Precautions will be taken to minimize anxiety, fear, and embarrassment. Women will be informed about the study prior to entry. Women will understand that they may terminate participation in this study at any time during the interview. They will also have the opportunity to decline to answer questions that are objectionable to them.

The proposed research may present possible risk to confidentiality because follow-up interviews require monitoring of the participant's address and telephone number. Participants will be given an identification code to separate identifying information from responses. Personnel involved with the interviewing will be educated about the importance of confidentiality. All identifying information will be destroyed following the final interview. Analyses will include only summaries of data and datasets with personal identifiers removed.

The proposed research does involve slight emotional or psychological risk. Precautions will be taken to minimize these risks through: 1) thoroughly explaining the study initially, 2) emphasizing that participation is voluntary, 3) allowing the participant to stop at any time during the interview, 4) using well-trained female interviewers and nurse counselors, and 5) coding data for confidentiality.

Indiana University has procedures in place to fulfill the NIH requirement for education in the Protection of Human Research Subjects. All grant personnel involved in the design or conduct of research involving human subjects on this project have or will complete this required education prior to the initiation of this project.

3. Potential Benefits of the Proposed Research to Subjects and Others

All participants will benefit monetarily because each will receive \$60 in gift cards for fully completing the study (\$20 for baseline and each of two telephone or electronic data collection interviews). In addition, participants may benefit from gaining knowledge about CRC and mammography screening. We will utilize the gift card service offered by Hallmark Business Connections.

4. Importance of knowledge to be gained: The research will indirectly benefit all women by testing interventions that may be related to BC and CRC screening behaviors in the population at greatest risk for CRC and BC, those 50 or older. Study findings may be used by health professionals to deliver new, more effective interventions to increase both CRC and BC screening.

Women and Minority Inclusion in Clinical Research:

By virtue of the nature of this study, all study participants will be women. Women will be recruited through their physician's medical records. Of these we estimate we will need to contact 5232 to yield 2616 participants who will be randomized, after consent, to one of three intervention groups and a usual care group. A letter of support is included in this application.

Inclusion of Children

The research topic to be studied is not relevant to children.

Data Safety and Monitoring Plan

Graduate research assistants will be extensively trained and monitored throughout the project to conduct computer-assisted telephone interventions (interviewers) and deliver assistance with the group completing the TIWeb program. Initial training will be conducted during a two-day session. The first day will consist of presentations including the following: 1) overview of grant objectives and rationale; 2) detailed demonstration of two intervention arms; 3) background and training on collecting data free from bias; 4) basic information on scale and item response issues; 5) protection of human subjects and confidentiality issues; and 6) data and intervention monitoring and quality assurance procedures. The second day will begin with a demonstration of

data collection using computer-assisted telephone interviewing. Following this initial demonstration, interviewers will role-play with videotaped feedback until they have reached 100% compliance with guidelines for data collection integrity. Research assistants who provide technical assistance to women needing help to use the TIWeb in their homes will be trained to assist with use of the TIWeb without providing additional education or information. They will practice and role-play until they have reached 100% compliance with guidelines for intervention delivery.

Quality Assurance for Intervention Delivery

Quality assurance and monitoring for integrity of intervention delivery are described in the previous section and in the Process Evaluation section of the proposal. Procedures for monitoring outcome data collection are described below. [name] will be responsible for oversight of monitoring quality assurance for intervention delivery, outcome data collection, and technical support.

Quality Assurance for Outcome Data Collection

After data collection begins, data collectors/interviewers will be part of the biweekly research team meetings that include the investigators, project managers, and research assistants to discuss project implementation and address questions or concerns that have arisen in the previous two weeks. All interviewers will be required to record one telephone interview each month; these interviews will be reviewed by the project manager and the investigators for quality assurance purposes. An evaluation checklist has been developed to assess the quality of data collection interviews and adherence to study protocol. Interviewers will be trained to query participants who have reported an abnormal mammogram to ensure prompt medical follow-up.

Quality Assurance for Data Managers

Data management will be handled by biostatisticians in the Indiana University, School of Medicine, Department of Medicine, Division of Biostatistics. Data monitoring will occur weekly as data from each interviewer are merged with the larger data set. Biostatisticians will handle all data merging. Backup data files will be kept in the Principal Investigator's office as well as the office of the biostatisticians. Interviewers will complete a form each week when sending data to be merged. The form will alert the biostatisticians to any abnormalities in the data set. All computers that will be used to collect and send data during implementation of the study or to store data at the central secured location will be password-protected.

Data integrity and security

IUPUI-Clarian Institutional Review Board approvals and related documents as well as all signed informed consent forms will be kept at Indiana University, School of Nursing in a locked location. All computers will be password-protected. Only trained grant personnel will have access to data. Once all data have been linked together for individuals, identifiers will be deleted from the data base that includes interview and mammography data. Identifiers will be kept in separate locked files from the collected data and used only for follow-up data collection. At the end of the study all identifiers will be deleted.

Identification of Adverse Effects

The principal investigators will monitor adverse events. First, adverse events will be monitored through the interviewers. Any concern will be brought to the attention of the principal investigators and, if immediate action is necessary, it will be undertaken and later discussed at team meetings. Adverse events will also be immediately reported to the IUPUI-Clarian Institutional Review Board. Participants will have a phone number to call if problems occur. Indiana University has a process in place whereby random monitoring for data integrity will occur by a committee external to the grant staff.

Data Sharing Plan

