For women who are nonadherent to CRC screening guidelines but adherent to BC screening (Group A), the TIWeb and the CSC will encourage CRC screening by building on the women's success with regular BC screening. For women who are nonadherent to both CRC and BC screening (**Group B**), the TIWeb and the CSC interventions will promote both CRC and BC screening simultaneously. Research indicates that individuals who undergo one type of cancer screening are more likely to pursue other forms of screening,⁽¹³⁾ making a holistic approach to cancer screening efficient and consistent with what would happen in a routine preventive care visit. In the proposed study, we also will test the cost-effectiveness of each intervention arm and the intervention interactions with demographic and practice variables. Past research^(14, 15) has shown that interventions vary in both cost and efficacy, making the addition of cost-effectiveness analysis important for future translation to practice. We will use a 2X2 factorial design with women randomly assigned to receive one of the following: 1) usual care, 2) a TIWeb, 3) a Cancer Screening Call (CSC), or 4) a TIWeb plus a CSC.

Aim 1: Compare the efficacy (adherence and stage) of four conditions to promote CRC and BC screening among women ages 50 to 75: 1) usual care; 2) a mailed TIDVD; 3) a CSC, and 4) a mailed TIDVD + a CSC. All women will be non adherent to CRC screening and may or may not be adherent to BC screening. 50 **Group A (nonadherent to CRC screening guidelines but adherent to BC screening guidelines)**

Hypothesis 1 (Primary outcome): There will be differences in CRC screening adherence and stage of adoption, when controlling for adherence to BC screening at baseline, among women who are randomized to 1) usual care; 2) a TIWeb; 3) a CSC, and 4) a TIWeb plus a CSC.

Group B (nonadherent to both CRC and BC screening guidelines)

Hypothesis 2 (Secondary outcome): In the group that is nonadherent to both CRC and BC screening at baseline, there will be differences in adherence to both CRC and BC screening and stage of adoption, among women who are randomized to 1) usual care; 2) a TIWeb; 3) a CSC, and 4) a TIWeb plus a CSC.

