An important component of this proposal is the estimation of the efficacy and cost-effectiveness of interactive interventions tailored to beliefs and stage of adoption alone and together. Similar to other studies, the outcome to be compared in the cost-effectiveness analysis is the proportion of participants in each of the intervention arms who have had recommended CRC or BC screening tests during the six-month period following initial intervention. Using this design, we will be able to determine if aTIWeb, a CSC, or a TIWeb+ CSC will significantly increase adherence for CRC and/or BC screening and at what costs. If efficacy and cost effectiveness relative to other interventions are demonstrated with the TIWeb program, it could be promoted at health care visits. If the CSC increases screening at an acceptable incremental cost when added to the TIWeb, office staff could make telephone counseling calls to participants from the health care setting after the TIWeb.

B.9. Researchers have tested the effectiveness of intervening simultaneously for multiple health behaviors. In 2005, Emmons et al. reported that a telephone-delivered intervention which focused on six behavioral risk variables for colorectal cancer was effective in promoting change.⁽¹⁰²⁾ In a different research study, a home-based intervention to change smoking, high fat diet, and sun exposure produced significant changes as compared to a control.⁽¹⁰³⁾ Recently, a series of articles addressed multiple behavior research.⁽⁵⁾ Behaviors included weight management, smoking, exercise, and fruit and vegetable intake.⁽¹⁰⁴⁻¹⁰⁶⁾ All interventions that addressed multiple behavior change were effective.

[figure not shown]

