D.12. Sample Size and Power Analysis: The *primary efficacy hypothesis in this area of research is adherence to screening. Therefore, adherence to CRC and BC screening at 6 months has driven our choice of sample size.* Originally, we proposed conducting analysis with two separate groups based on initial mammography status: 1) women who were adherent to mammography but not to colorectal cancer (CRC) screening, and 2) women who were adherent to neither mammography nor CRC screening. By testing these groups separately, we required a sample size of 2616 to achieve 80% power between both the control and intervention groups and between any combinations of groups. In re-considering this approach, we realized that since the outcome of CRC screening was common across both groups A and B, this was not the most efficient design to test our outcomes. We are proposing analyses using one group of women, all of whom will be non-adherent to CRC screening at baseline. In this group, some women will be adherent to mammography guidelines (i.e., had a mammogram in the past 15 months) and others will be non adherent. For Aim 1, when we examine intervention effects on the outcome of CRC screening, we will control for baseline adherence to mammography. For Aim 2, we will use only the sub-group of women who were not adherent to either breast or CRC screening at baseline. Using this approach will reduce the sample size needed and reduce the overall costs of the study, more closely aligning the budget with the amount awarded. Most importantly, revising our analytical approach will enable us to achieve our initial Aims despite the reduced sample size.

Specifically, for the outcome of CRC screening adherence, we had justified sample size in the original proposal to achieve 80% power to detect differences between intervention groups, *separately* for two groups of women depending on their baseline breast cancer screening adherence status.

Group A includes women who were nonadherent to CRC screening but adherent to BC screening, and **Group B** includes women nonadherent to both CRC and BC screening.

We realize now that it is unnecessary to perform the analysis of CRC adherence separately for the two groups (A and B). Instead the Group variable (A vs B) can be entered in the model using baseline mammography screening as a covariate.

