In Table 8 of the original application (see appendix), we proposed enrolling 327 for each of 8 combinations of 4 arms and 2 groups (A and B) for a study total of 2616. However, using this alternative approach will require only 1308 (327 in each of the 4 arms) women to test the primary outcome of CRC adherence. However, new studies, including our own, indicate 15-20% adherence to CRC screening in control conditions. Our initial proposal anticipated on 10% adherence in the control arm. Thus, although the new design decreases the sample size by combining the groups, a more realistic estimate of the adherence in the control group will actually increase the sample size compared to our estimate in Group A for the initial proposal. Specifically, we propose to increase our estimate of CRC adherence in all four arms, to accommodate a change in the proposed adherence in the control group from 10% to 20%. This will require 397 instead of 327 per arm (see Table 1). Thus, a sample of 397 per group at baseline (357 per group at 6 months after 10% estimated attrition) will provide 80% power to detect differences between any pair of the four randomized arms for Aim 1 (Table 1).

Revised Sample size and Power analysis for primary efficacy hypothesis of estimated CRC screening adherence rates in the combined groups of those adherent (Group A) and non-adherent (Group B) at baseline to breast cancer screening (Aim 1, primary outcome of CRC adherence)

GROUPS A and B combined

Time	Usual Care (1)	TIDVD (2)	CSC (3)	TIDVD+CSC (4)	Power
Baseline adherence	0%	0%	0%	0%	NA
Total sample size (N):	(n = 397)	(n = 397)	(n = 397)	(n = 397)	
N by baseline strata, Adherent to BC (A) Non-adherent to BC (B)	(n = 119) (n = 278)				
6 months adherence	20%	30%	40%	55%	Power for 357/arm (Groups A and B combined)
Total sample size (N):	(n = 357)	(n = 357)	(n = 357)	(n = 357)	1v2 .87 1v3 .99 1v4 .99 2v3 .80 2v4 .99 3v4 .98
N by baseline strata, Adherent to BC (A) Non-adherent to BC (B)	(n = 107) (n = 250)				

Enrollment will be stratified by women adherent to breast but not CRC screening and those adherent to neither in a 30%/70% ratio so that we will have an adequate sample to detect an 80% power for Aim 2. Aim 2 will use only the subgroup of women who are not adherent to either breast or CRC screening. This will provide at least 80% power for Group B for comparing each pair of randomized arms, when testing the secondary outcome (adherence to both CRC and BC screening) (Table 2).

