Bundling screening promotion services to promote multiple screening tests for women in group B presents a special cost problem due to the difficulty of allocating cost to specific outcomes. The main difference in cost between participants in **Group A** and those in **Group B** will be participant time and telephone counseling time required to communicate information about two versus one type of screening. These costs will be directly allocated to the screening interventions by tracking time for each participant. Other implementation costs will be the same for subjects eligible for either one test or two screening tests (e.g., recruitment). For group B, we follow methods employed by Chirikos et al. (2004)⁽¹⁴³⁾ to adjust the cost estimate for subjects eligible for two screening tests. In their study of an office-based primary care tracking system to increase screening for breast, cervical, and colorectal cancer, they apportioned the cost to subjects based on the number of tests they were eligible for. If a participant was eligible for two screening tests, they were assigned ½ of the intervention cost and the full intervention cost if they were eligible for only one test. Thus, cost for participants in group B will consist of directly allocated cost for their time and nurse counselor time and other costs apportioned by the number of tests for which they are eligible (see equations below).

Cost-effectiveness Analysis: The cost-effectiveness evaluation is examined from the societal perspective and from the more limited perspective of the provider to inform future decision-makers about the relative efficiency of the alternative interventions. The analysis focuses on the incremental cost per additional individual who is adherent (i.e., has a CRC, BC, or both screening tests during the observation period) for each alternative intervention. The intervention costs will include participant time costs and resource costs and be

valued in 2010 constant U.S. dollars. This focus is consistent with the recommendations of the Report of the Expert Panel on Cost-Effectiveness in Health and Medicine.⁽¹⁴⁴⁾ The base case will be defined as the estimate of costs and effects derived from the best point estimate of intervention parameters. Planning, implementation, and participant costs will be tracked for the interventions.

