The primary cost-effectiveness measures will be the incremental cost-effectiveness ratios (ICERs) obtained by dividing the additional per target individual cost by the additional percent of target individuals who are screened by the end of the follow-up period, comparing the control group to the TIWeb group, to the CSC group, to the TIWeb+CSC group moving from the least resource-intensive to the most resource-intensive interventions (equations 1,2,3). These measures will be based on intention to treat methods and correspond to the observation period of the study.⁽¹⁴⁵⁾

Group A (cost fully allocated to BCS intervention)

- 1) $ICER_1 = (Cost_{TIWeb} - Cost_{UC}) \div (\%BCS_{TIWeb} - \%BCS_{UC})$
- 2) $ICER_2 = (Cost_{CSC} - Cost_{TIWeb}) \div (\%BCS_{CSC} - \%BCS_{TIWeb})$
- 3) $ICER_3 = (Cost_{TIWeb+CSC} - Cost_{CSC}) \div (\%BCS_{TIWeb+CSC} - \%BCS_{CSC})$

Group B (cost adjusted for joint production)

BCS: (directly allocated plus 1/2 of non directly allocated cost applied to BCS intervention)

- 1) $ICER_1 = (Cost_{TIWeb} - Cost_{UC}) \div (\%BCS_{TIWeb} - \%BCS_{UC})$
- 2) $ICER_2 = (Cost_{CSC} - Cost_{TIWeb}) \div (\%BCS_{CSC} - \%BCS_{TIWeb})$
- 3) $ICER_3 = (Cost_{TIWeb+CSC} - Cost_{CSC}) \div (\%BCS_{TIWeb+CSC} - \%BCS_{CSC})$

CRC: (directly allocated plus 1/2 of non directly allocated cost assigned to CRCS intervention)

- 1) $ICER_1 = (Cost_{TIWeb} - Cost_{UC}) \div (\%CRCS_{TIWeb} - \%CRCS_{UC})$
- 2) $ICER_2 = (Cost_{CSC} - Cost_{TIWeb}) \div (\%CRCS_{CSC} - \%CRCS_{TIWeb})$
- 3) $ICER_3 = (Cost_{TIWeb+CSC} - Cost_{CSC}) \div (\%CRCS_{TIWeb+CSC} - \%CRCS_{CSC})$

BCS & CRCS: (all costs allocated to joint BCS & CRCS intervention)

- 1) $ICER_1 = (Cost_{TIWeb} - Cost_{UC}) \div (\%BCS \& CRCS_{TIWeb} - \%BCS \& CRCS_{UC})$
- 2) $ICER_2 = (Cost_{CSC} - Cost_{TIWeb}) \div (\%BCS \& CRCS_{CSC} - \%BCS \& CRCS_{TIWeb})$
- 3) $ICER_3 = (Cost_{TIWeb+CSC} - Cost_{CSC}) \div (\%BCS \& CRCS_{TIWeb+CSC} - \%BCS \& CRCS_{CSC})$

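### No planned cost-effectiveness ratio prices the primary outcome, CRC screening in Groups A and B combined, and the Group A ratios divide by breast instead of CRC screening

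*Combined protocol and SAP*

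**What the plan says.** **Primary outcome.** Hypothesis 1 (Section A, repeated at the end of D.12) reads "There will be differences in CRC screening adherence and stage of adoption, when controlling for adherence to BC screening at baseline". D.12 explains the redesign: "We realize now that it is unnecessary to perform the analysis of CRC adherence separately for the two groups (A and B"), with group entering the model as a covariate. The trial is sized on the two groups together: "a sample of 397 per group at baseline (357 per group at 6 months after 10% estimated attrition"). Enrolment is stratified by baseline mammography status "in a 30%/70% ratio" (A to B).

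**Cost-effectiveness in words.** B.8 states that "the outcome to be compared in the cost-effectiveness analysis is the proportion of participants in each of the intervention arms" who have had CRC or BC screening within six months, so that the trial can say which intervention works and what it costs. D.13 (Aim 2, Cost-effectiveness Analysis) likewise works per intervention and counts a woman as adherent if she "has a CRC, BC, or both screening tests during the observation period".

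**Cost-effectiveness in equations.** D.13 continues: "The primary cost-effectiveness measures will be the incremental cost-effectiveness ratios (ICERs"), taken stepwise from usual care to website, website to call, and call to combination. The equations are:
- Group A: three ratios, all cost assigned to breast screening, with %BCS in the denominator.
- Group B: three ratios each for %BCS, %CRCS, and both tests together.

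**Outcome by group.** D.13 (Program Effectiveness) gives CRC screening as the outcome for Group A, and CRC, BC and both for Group B.

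Uncertainty is to be shown by bootstrap samples and scatter plots. No precision target is set for any ratio.

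**The concern.** The redesign reached the hypothesis and the power section but not the cost equations. If the website or the call raises CRC screening in the primary analysis, no planned ratio gives the cost per additional woman screened for that result. A reader would have to work from ratios on 30% and 70% of the women, neither of which is the population of the primary comparison.

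The Group A equations add a second fault. Their denominator is an outcome on which these women were already adherent at entry, and it is not the outcome that D.13 assigns to them. Followed literally, the plan prices CRC screening in Group B only, with half of the shared cost. This matters because B.8 ties uptake in practice to an acceptable incremental cost.

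**Working it through.** **Inputs (D.12).** Planned 6-month CRC rates are 20% (usual care), 30% (website, labelled TIDVD in the table), 40% (call) and 55% (combination). They are given for A and B combined only. Numbers per arm at 6 months are 357 combined, 107 in Group A and 250 in Group B. The limitations part of D.13 supports the dropout figure: "We are conservatively estimating a 10% loss to follow-up".

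**The plan's own figures.** 397 x 0.9 = 357.3; 357 x 0.30 = 107.1; 357 x 0.70 = 249.9. A two-sided 5% comparison of two proportions at 357 per arm, without continuity correction, gives power .871 (20 v 30%), .801 (30 v 40%) and .981 (40 v 55%). The table states .87, .80 and .98. The plan does not state alpha for this test; two-sided 0.05 is assumed and reproduces its figures.

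**Precision of each stepwise effect.** SE = sqrt[(p1(1-p1) + p2(1-p2))/n]; limits = difference +/- 1.96 SE.
- 20 v 30%: SE = sqrt(0.37/n) = 0.0588 (n = 107), 0.0385 (250), 0.0322 (357).
- 30 v 40%: SE = sqrt(0.45/n) = 0.0649, 0.0424, 0.0355.
- 40 v 55%: SE = sqrt(0.4875/n) = 0.0675, 0.0442, 0.0370.

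The same rates are assumed in each group. Limits are in percentage points:

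| Step | Effect | Group A, 107 | Group B, 250 | Combined, 357 |
|---|---|---|---|---|
| Usual care to website | 10 | -1.5 to 21.5 | 2.5 to 17.5 | 3.7 to 16.3 |
| Website to call | 10 | -2.7 to 22.7 | 1.7 to 18.3 | 3.0 to 17.0 |
| Call to combination | 15 | 1.8 to 28.2 | 6.3 to 23.7 | 7.8 to 22.2 |

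The Group A column applies only after %CRCS replaces the printed %BCS.

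**What this does to the ratio.** With incremental cost held fixed, the limits of the ratio, as multiples of its point value, are difference/upper limit to difference/lower limit:

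| Step | Group A | Group B | Combined |
|---|---|---|---|
| Usual care to website | 0.46 to no finite limit | 0.57 to 4.07 | 0.61 to 2.71 |
| Website to call | 0.44 to no finite limit | 0.55 to 5.94 | 0.59 to 3.29 |
| Call to combination | 0.53 to 8.47 | 0.63 to 2.36 | 0.67 to 1.93 |

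Analysing all 119 randomised Group A women per arm does not change the finding: the first two effects become -0.9 to 20.9 and -2.1 to 22.1.

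**The cost rule in a combined ratio.** D.13 charges Group A the full cost, and Group B its directly allocated cost plus half of the rest for each test. At the enrolled mix the combined numerator therefore carries 0.30 x 1 + 0.70 x 0.5 = 0.65 of the shared cost per woman. Charging Group B in full gives 1.00, so the shared component rises by a factor of 1/0.65 = 1.54.

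**The case against.** The strongest reply is that separate ratios are a reasoned choice. Aim 2 names both groups, D.13 sets outcomes by group, and it explains that promoting two tests at once makes cost allocation difficult. A combined numerator mixes full cost in A with half of shared cost in B, so it depends on an accounting convention and is not simply what a practice would spend. That stands as a reason to keep the group ratios and to show a full-cost version. It does not explain why the primary outcome has no ratio: Aim 2 includes both groups without barring a combined figure, and the plan's rule already yields a CRC cost for every woman.

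It can also be said that the two-group layout is not peculiar to the cost section, since D.13 still files Hypothesis 1 under a Group A heading for Aim 1. That is true, but the hypothesis and the sample size settle that the primary outcome is combined.

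Two stronger readings are tempting. A reader might infer that the Group A ratios are too imprecise to use. The documents do not support that. They give no precision target and no Group A rates, the bootstrap would display the uncertainty, and contrasts with usual care in Group A would be tighter (call 0.63 to 2.49 times the point value, combination 0.74 to 1.53), though those are not the planned steps. A reader might also infer that a combined ratio should be reweighted to the practice mix in Section A, 26/(26 + 44) = 37% Group A. That would again separate the cost population from the 30:70 efficacy population. It also rests on a records review that does not reflect the high-speed Internet criterion in D.2.

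**Conclusion.** The mismatch is established by the text: twelve primary ratios, none on CRC screening in A and B combined, and three with a denominator that contradicts the plan's own statement of the Group A outcome. It should be corrected, but it does not leave the trial without a CRC cost answer. Group B has printed CRC ratios, and at the planning rates all three of their effect intervals exclude zero.

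The gain from a combined ratio is moderate and concrete: all three stepwise ratios become bounded, against one of three in Group A once its outcome is corrected. That size rests on three assumptions: the combined planning rates hold in each group, incremental cost is fixed, and normal-approximation limits are used.

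**What to change.** In D.13, Cost-effectiveness Analysis:
1. Add the three stepwise ratios on %CRCS in Groups A and B combined, in the enrolled mix used for the primary efficacy analysis, and name them as the cost-effectiveness result that matches the primary outcome.
2. State the numerator: full cost for Group A; directly allocated plus half of other cost for Group B. Add a sensitivity analysis charging full cost in Group B, which the plan already computes for its both-tests ratio.
3. Change the Group A equations and their cost label from BCS to CRCS.
4. Keep the group-specific ratios alongside, and align the outcome wording in B.8 and D.13 with the equations.

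The cost is SAP wording and one more set of ratios from data already collected. The downside is that the combined ratio averages two groups with different costs and depends on the allocation convention; the group ratios and the sensitivity analysis make both visible.
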